9.4.4. Safety Analysis

Safety data will be presented in tabular and/or listing format and summarized descriptively. Number and percentage will be presented for incidence of AE.

Descriptive statistics (N, n, mean, SD, median, minimum and maximum) will be presented for absolute and change from baseline values of vital signs parameters at each timepoint.

Comprehensive description for statistical analyses of safety endpoints will be described in the SAP.

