3.4 Randomization

Participants will be assigned either of the two sequence 'TRTR' or 'RTRT' based on the randomization schedule by Lambda generated using SAS® Version 9.4 or higher (SAS Institute Inc., USA). Equal allocation of participants in each sequence is planned.

The personnel involved in dispensing of study intervention and verification of dispensed study interventions will be accountable for ensuring compliance to randomization schedule.

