7.2 Safety Analysis

Safety analysis will be done on the safety set. Safety variables include AEs, clinical laboratory parameters, vital signs, physical examinations. Safety variables will be listed and summarized with descriptive statistics as appropriate.

Continuous variables will be Summarized by treatment/sequence group using summary statistics (number of observations, mean, standard deviation, median, minimum and maximum etc.) as applicable. Categorical values will be summarized by the treatment group using frequencies and percentages.

Result obtained when evaluating safety (adverse events, vital signs, clinical laboratory tests etc.) will be listed and evaluated descriptively.

Adverse events

All AEs reported during the study must be included in the safety analysis. AEs will be classified by system organ class, by preferred term from the MedDRA version 25.0 or higher. They will be presented in individual listings and summary tables, and evaluated descriptively and in terms of

frequencies, by treatment. As will be summarized for all subjects in Safety set across two treatment groups by System Organ Class (SOC) and Preferred Term (PT). p-value using chi-square test or fisher exact test will be provided for the AE data.

Intensity refers to the severity of the AE.: Mild, Moderate, Severe.

Clinical laboratory values

LAMBDA

Clinical laboratory values will be compared to their reference ranges. Values outside the normal ranges will be highlighted. The Investigator has to comment, whether the abnormality is clinically relevant.

Other safety parameters

All results of vital sign measurements will be presented in individual listings. Where appropriate, results and possible changes in parameters will be evaluated descriptively or by descriptive statistics (mean, SD, median, range). Descriptive statistics (N, n, mean, SD, median, minimum and maximum) will be presented for absolute and change from baseline values of vital signs parameters at each timepoint.

Demographic data will be shown in tables as mean values, SD and ranges (min, max).

Clinical laboratory data will be shown in tables as mean values, SD and ranges (min, max) as applicable.

Physical examination, 12 lead ECG, Chest X-Ray performance and concomitant medication will be presented in data listings.

Protocol deviations

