14.3 Safety Data

14.3.1 Overall summary of treatment emergent adverse events (Safety set)

Lambda Therapeutic Research Ltd.

Confidential

Project No. 0110-23

Table 14.3.1

	Test Treatment-T	Reference Treatment-R	Total	
	(N=xx)	(N=xx)	(N=xx)	p-valu
	n (%) e	n (%) e	n (%) e	
At least one TEAE	xx (xx.x) xx	xx (xx.x) xx	xx (xx.x) xx	x.xxx
At least one TEAE leading to discontinuation	xx (xx.x) xx	xx (xx.x) xx	xx (xx.x) xx	X.XXX
At least one TESAE	xx (xx.x) xx	xx (xx.x) xx	xx (xx.x) xx	_
Assessment of intensity				_
Mild	xx (xx.x) xx	xx (xx.x) xx	xx (xx.x) xx	
Moderate	xx (xx.x) xx	xx (xx.x) xx	xx (xx.x) xx	
Severe	xx (xx.x) xx	xx (xx.x) xx	xx (xx.x) xx	
Seriousness criteria				-
Congenital Anomaly/Birth Defect	xx (xx.x) xx	xx (xx.x) xx	xx (xx.x) xx	
Hospitalization or prolongation of existing	xx (xx.x) xx	xx (xx.x) xx	xx (xx.x) xx	
hospitalization	xx (xx.x) xx	xx (xx.x) xx	xx (xx.x) xx	
Result in persistent or Significant	xx (xx.x) xx	xx (xx.x) xx	xx (xx.x) xx	
Disability/incapacity	AA (AA.A) AA	AA (AA.A) AA	AA (AA.A) AA	
Life threatening	xx (xx.x) xx	xx (xx.x) xx	xx (xx.x) xx	
Abnormal pregnancy outcomes	xx (xx.x) xx	xx (xx.x) xx	xx (xx.x) xx	
Death	xx (xx.x) xx	xx (xx.x) xx	xx (xx.x) xx	
Other Medically Important Event	xx (xx.x) xx	xx (xx.x) xx	xx (xx.x) xx	
Relationship to Study Treatment				_
Related				
Certain	xx (xx.x) xx	xx (xx.x) xx	xx (xx.x) xx	
Probable/Likely	xx (xx.x) xx	xx (xx.x) xx	xx (xx.x) xx	
Possible	xx (xx.x) xx	xx (xx.x) xx	xx (xx.x) xx	
Not Related				
Unlikely	xx (xx.x) xx	xx (xx.x) xx	xx (xx.x) xx	
Conditional/Unclassified	xx (xx.x) xx	xx (xx.x) xx	xx (xx.x) xx	

Lambda Therapeutic Research Ltd.

Confidential Table 14.3.1

Project No. 0110-23

Overall summary of treatment emergent adverse events (Safety set)

	Test Treatment-T	Reference Treatment-R	Total	
	(N=xx)	(N=xx)	(N=xx)	p-value
	n (%) e	n (%) e	n (%) e	
Unassessable/Unclassifiable	xx (xx.x) xx	xx (xx.x) xx	xx (xx.x) xx	
Unrelated	xx (xx.x) xx	xx (xx.x) xx	xx (xx.x) xx	
Action Taken with Study Treatment				_
Dose Increased	xx (xx.x) xx	xx (xx.x) xx	xx (xx.x) xx	
Dose Not Changed	xx (xx.x) xx	xx (xx.x) xx	xx (xx.x) xx	
Dose Reduced	xx (xx.x) xx	xx (xx.x) xx	xx (xx.x) xx	
Drug Interrupted	xx (xx.x) xx	xx (xx.x) xx	xx (xx.x) xx	
Drug Withdrawn	xx (xx.x) xx	xx (xx.x) xx	xx (xx.x) xx	
Not Applicable	xx (xx.x) xx	xx (xx.x) xx	xx (xx.x) xx	
Unknown	xx (xx.x) xx	xx (xx.x) xx	xx (xx.x) xx	
Outcome				_
Not Recovered/Not Resolved	xx (xx.x) xx	xx (xx.x) xx	xx (xx.x) xx	

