Recovering/resolving	xx (xx.x) xx	xx (xx.x) xx	xx (xx.x) xx	
Recovered/Resolved	xx (xx.x) xx	xx (xx.x) xx	xx (xx.x) xx	
Recovered/Resolved With Sequelae	xx (xx.x) xx	xx (xx.x) xx	xx (xx.x) xx	
Stable	xx (xx.x) xx	xx (xx.x) xx	xx (xx.x) xx	
Change in severity	xx (xx.x) xx	xx (xx.x) xx	xx (xx.x) xx	
Fatal	xx (xx.x) xx	xx (xx.x) xx	xx (xx.x) xx	
Converted to SAE	xx (xx.x) xx	xx (xx.x) xx	xx (xx.x) xx	
Unknown	xx (xx.x) xx	xx (xx.x) xx	xx (xx.x) xx	
Death	xx (xx.x) xx	xx (xx.x) xx	xx (xx.x) xx	

N = Number of subjects in respective treatment population.

Reference Listing: 16.2.7.1

n = Number of subjects in respective categories; e = Number of events.

Percentages are based on the number of subjects allocated to each category.

P-value is calculated based on a chi-square test. If any cell has expected counts less than 5, then the Fisher's exact test is used instead.

14.3.2 Summary of treatment emergent adverse events by system organ class and preferred term (Safety set)

Lambda Therapeutic Research Ltd.

Confidential

Project No. 0110-23

Table 14.3.2

Summary of treatment emergent adverse events by system organ class and preferred term (Safety set)

	Test Treatment-T	Reference Treatment-R	Total
System Organ Class	(N=xx)	(N=xx)	(N=xx)
Preferred Term	n (%) e	n (%) e	n (%) e
Subjects with At least one TEAE	xx (xx.x) xx	xx (xx.x) xx	xx (xx.x) xx
System Organ Class 1	xx (xx.x) xx	xx (xx.x) xx	xx (xx.x) xx
Preferred Term 1	xx (xx.x) xx	xx (xx.x) xx	xx (xx.x) xx
Preferred Term 2	xx (xx.x) xx	xx (xx.x) xx	xx (xx.x) xx
•			
•			
System Organ Class 2	xx (xx.x) xx	xx (xx.x) xx	xx (xx.x) xx
Preferred Term 1	xx (xx.x) xx	xx (xx.x) xx	xx (xx.x) xx
Preferred Term 2	xx (xx.x) xx	xx (xx.x) xx	xx (xx.x) xx
Etc.			

N = Number of subjects in respective treatment population.

n = Number of subjects in respective categories; e = Number of events.

Percentages are based on the number of subjects allocated to each category.

Each subjects is counted at the most once within each PT.

Adverse Events are coded using Medical Dictionary for Regulatory Activities (MedDRA) version xx

Reference Listing: 16.2.7.1

Project No. 0110-23 Version 00

14.3.3 Summary of treatment emergent adverse events by relationship to study drug and system organ class and preferred term (Safety set)

Lambda Therapeutic Research Ltd.

Confidential

Project No. 0110-23

Table 14.3.3

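### The AE p-value planned in SAP 7.2 and Table 14.3.1 treats Test and Reference as independent groups, although participants dosed with both products are counted in both columns

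*SAP*

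**What the plan says.** SAP 3.4: "Participants will be assigned either of the two sequence 'TRTR' or 'RTRT' based on the randomization schedule". A completer therefore takes Test twice and Reference twice. The Safety set (SAP 4) is everyone randomized who received at least one dose.

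SAP 7.2 asks for AEs to be summarised on the Safety set by treatment and adds that a "p-value using chi-square test or fisher exact test will be provided for the AE data". The shell of Table 14.3.1 has Test, Reference, Total and p-value columns. Its footnotes say "N = Number of subjects in respective treatment population" and "P-value is calculated based on a chi-square test", with Fisher's exact test if any expected count is below 5. The unit counted is the subject.

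Only two rows carry a p-value placeholder: at least one TEAE, and "At least one TEAE leading to discontinuation". Tables 14.3.2 to 14.3.4 have no p-value column. Neither document names a paired or crossover method for AEs, and neither sets a significance level for these p-values; the 5% in SAP 6.3.2.2 belongs to the PK ANOVA.

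Protocol 9.4.4 says "Safety data will be presented in tabular and/or listing format and summarized descriptively", with number and percentage for AE incidence, and leaves the full description to the SAP. SAP 7.2 also says that safety results are assessed descriptively.

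**The concern.** Chi-square and Fisher's test are derived for two separate sets of people. Here the two columns are largely the same people. The test sees only the two column totals. It cannot tell whether the participants with an AE on Test are the same ones who had an AE on Reference, and that is the information a crossover provides.

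Safety and tolerability of Test against Reference is a stated secondary objective, with AE incidence as an endpoint. If some participants are more prone to report AEs whichever tablet they take, the printed p-value will be too large. A reader who takes it at face value would then see less evidence of a product difference than the data hold, which is the less welcome direction in a safety table.

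**Working it through.** The documents give no figure for this test, so there is none to reproduce.

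**Inputs.** From the documents: 70 planned participants, 48 evaluable (SAP 3.3), and the test rule in the Table 14.3.1 footnote. Assumed, because the documents do not give them: AE incidence per product (pT, pR), within-participant correlation φ, a two-sided 5% level, and everyone dosed with both products.

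**Step 1: direction.** With equal incidence p on both products, the unpaired test uses variance 2p(1−p)/n for the difference in proportions. The true variance is 2p(1−p)(1−φ)/n. The approximate true size at nominal 5% is therefore 2[1 − Φ(1.96/√(1−φ))]: 5.0% at φ = 0, 2.8% at 0.2, 1.1% at 0.4 and 0.2% at 0.6.

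**Step 2: exact size.** All paired tables (both, Test only, Reference only, neither) were enumerated with P(both) = pT·pR + φ√[pT(1−pT)pR(1−pR)], so that the marginal incidences stay fixed. The SAP rule was taken as uncorrected chi-square, or Fisher if an expected count is below 5.

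| Size, 70 participants | φ=0 | 0.1 | 0.2 | 0.3 | 0.5 |
|---|---|---|---|---|---|
| SAP rule, 25% incidence | 5.1% | 4.0% | 3.0% | 2.0% | 0.6% |
| SAP rule, 10% incidence | 4.9% | 3.8% | 2.8% | 1.9% | 0.6% |
| Mid-p McNemar, 10% incidence | 4.4% | 4.3% | 4.1% | 4.0% | 3.2% |

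At 25% incidence mid-p McNemar stays at 4.4–4.6%, asymptotic McNemar at 4.5–5.4% and exact McNemar at 2.6–3.0%. With 48 participants at 25% the SAP rule gives 5.1, 4.0, 2.9, 2.0 and 0.7%.

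**Step 3: power, 45% v 25%.**

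| | φ=0 | 0.1 | 0.2 | 0.3 | 0.5 |
|---|---|---|---|---|---|
| SAP rule, n=70 | 71% | 72% | 73% | 74% | 78% |
| Mid-p McNemar, n=70 | 69% | 73% | 78% | 84% | 95% |
| Exact McNemar, n=70 | 63% | 67% | 73% | 79% | 93% |
| SAP rule, n=48 | 54% | 55% | 55% | 55% | 56% |
| Mid-p McNemar, n=48 | 51% | 56% | 62% | 68% | 83% |

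Pairing costs about 2 points with mid-p at φ = 0 (n=70) and pays once φ is positive. Exact McNemar gains only above φ = 0.2.

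**Step 4: low incidence.** With 70 in each column, Fisher applies when fewer than 10 AE-positive counts are seen in total, since the smaller expected count is half that total. At 5% on each product the expected total is 2 × 70 × 0.05 = 7, so Fisher is the usual case. The size is then 2.2% at φ = 0 and 1.1% at 0.2 (mid-p 3.4% and 2.7%). Much of that conservatism comes from Fisher's test rather than from pairing. Power for 10% v 5% is low either way: 18% and 15% with the SAP rule, 18% and 20% with mid-p.

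**Step 5: an illustration with invented counts.** Take 20/70 on Test and 11/70 on Reference. The SAP rule gives χ² = 140(20·59 − 11·50)²/(70·70·31·109) = 3.36, p = 0.067, whatever the overlap.
- If 8 participants had AEs on both (12 Test only, 3 Reference only), exact McNemar gives 2(1+15+105+455)/2¹⁵ = 0.035.
- If nobody had AEs on both (20 Test only, 11 Reference only), exact McNemar gives 0.15.

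**Step 6: the discontinuation row.** Its denominators overlap in the same way. Whether a participant can be in both numerators depends on what counts. Protocol 7.1.1 and 7.2 allow discontinuation or withdrawal for a particular period as well as from the study, and the SAP does not say whether period-only withdrawals enter this row.

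**The case against.** The best case for leaving the plan alone is that the stakes are very small. Two cells in one table are affected, no decision depends on them, and under positive correlation the error is conservative. That stands and sets the weight of the point, but it does not make the named test suit the design. It is also true that the larger power gains need correlations of 0.3 to 0.5, which the documents neither support nor exclude. Protocol 2.3 expects the label risks to be unlikely in this population; that statement is qualitative and does not cover all AEs, but it makes the low-incidence case in step 4 relevant.

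Four stronger readings are tempting, and the documents do not support them.

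- *The test inflates false positives.* With positive correlation it does the opposite for at least one TEAE, and at zero correlation the size is about nominal at 10–25% incidence.
- *Nobody can be in both numerators of the discontinuation row, so its error runs the other way.* The row label does not say permanent, and period-only withdrawal is allowed. If only study discontinuation counts, the enumerated size with no overlap is 2.6% at 5% incidence (2.2% if independent) and 6.2% at 10% (4.9% if independent). The 10% case is strained: it means 20% of participants stopping for AEs, against about 30% dropout planned for all reasons. It also puts 70 in each denominator, although someone who stops after period I has taken one product only.
- *The independent t-tests in Tables 14.1.1 and 14.3.6 share the fault.* They compare the TRTR and RTRT groups, which are different people, and SAP 7.2 allows this grouping: "Continuous variables will be Summarized by treatment/sequence group using summary statistics".
- *The SAP breaches the protocol by adding a test.* Protocol 9.4.4 hands the detail of the safety analysis to the SAP, so an added p-value is not a contradiction.

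**Conclusion.** Wrong as written, and minor. SAP 7.2 and the Table 14.3.1 footnote prescribe an independent-groups test for columns that share every participant dosed with both products.

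For at least one TEAE, the size at nominal 5% drops from about 5% to about 3% at correlation 0.2 and 0.6% at 0.5 (70 participants, 25% incidence), so the p-value understates evidence of a product difference when AEs cluster within people. That size rests on assumed incidence and correlation and on everyone receiving both products. That the pairing is ignored follows from the design and the table definitions alone. For the discontinuation row, only the overlap of denominators is certain; the direction of any error cannot be stated until the SAP says which withdrawals count. The bioequivalence conclusion does not depend on any of this.

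**What to change.** Preferred: delete the AE p-value sentence from SAP 7.2 and the p-value column and its footnote from Table 14.3.1. Keep counts and percentages by treatment. This matches the descriptive intent of SAP 7.2 and Protocol 9.4.4. The cost is one sentence, one column and one footnote, with no new data.

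If a p-value is wanted:
- limit it to at least one TEAE and give the discontinuation row as counts only;
- use mid-p or asymptotic McNemar, or a paired risk difference with a confidence interval;
- state that participants dosed with only one product stay in the counts but leave the test;
- state how participants with unequal numbers of Test and Reference doses are handled, since after three periods the row compares two doses of one product with one of the other.

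The price of the paired option is about 2 points of power for mid-p if the correlation is in fact zero (69% against 71% at 45% v 25%, 70 participants). The vital-signs tables need no change on this account.

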14.1 Demographic Data

14.1.1 Demographic data and baseline characteristics (Randomized set)

Lambda Therapeutic Research Ltd.

Confidential

Project No. 0110-23

Table No. 14.1.1

Demographic data and baseline characteristics (Randomized set)

	Statistics	TRTR (N=xx)	RTRT (N=xx)	Total (N=xx)	p-value
Age (years)	n	XX	XX	XX	X.XXXX
	Mean (SD)	xx.x (xx.xx)	xx.x (xx.xx)	xx.x (xx.xx)	
	Median	XX.X	XX.X	XX.X	
	Min, Max	XX.X, XX.X	XX.X, XX.X	XX.X, XX.X	
Gender					-
Male	n (%)	xx (xx.x)	xx (xx.x)	xx (xx.x)	
Female	n (%)	xx (xx.x)	xx (xx.x)	xx (xx.x)	
Race					
Asian	n (%)	xx (xx.x)	xx (xx.x)	xx (xx.x)	-
American Indian or Alaska Native	n (%)	xx (xx.x)	xx (xx.x)	xx (xx.x)	
Other	n (%)	xx (xx.x)	xx (xx.x)	xx (xx.x)	
Ethnicity					
Not Hispanic or Latino	n (%)	xx (xx.x)	xx (xx.x)	xx (xx.x)	_
Hispanic or Latino	n (%)	xx (xx.x)	xx (xx.x)	xx (xx.x)	
Not Reported	n (%)	xx (xx.x)	xx (xx.x)	xx (xx.x)	
Unknown	n (%)	xx (xx.x)	xx (xx.x)	xx (xx.x)	
Height (cm)	n	xx	xx	XX	x.xxxx
	Mean (SD)	xx.x (xx.xx)	xx.x (xx.xx)	xx.x (xx.xx)	
	Median	XX.X	XX.X	XX.X	
	Min, Max	xx.x, xx.x	XX.X, XX.X	xx.x, xx.x	

Project No. 0110-23 Version 00

Lambda Therapeutic Research Ltd.

Confidential

Project No. 0110-23

Table No. 14.1.1

Demographic data and baseline characteristics (Randomized set)

	Statistics	TRTR (N=xx)	RTRT (N=xx)	Total (N=xx)	p-value
Weight (kg)	n	XX	XX	XX	x.xxxx
	Mean (SD)	xx.x (xx.xx)	xx.x (xx.xx)	xx.x (xx.xx)	
	Median	XX.X	XX.X	XX.X	
	Min, Max	xx.x, xx.x	xx.x, xx.x	xx.x, xx.x	
BMI (kg/m²)	n	xx	xx	xx	x.xxx
	Mean (SD)	xx.x (xx.xx)	xx.x (xx.xx)	xx.x (xx.xx)	
	Median	XX.X	XX.X	XX.X	
	Min, Max	XX.X, XX.X	xx.x, xx.x	XX.X, XX.X	

N = Number of subjects in safety set, n = Number of subjects in respective categories Note: Percentages are calculated based on the total number of subjects in each category. Treatment specification -> T = Test Product and R = Reference Product. p-value is calculated using an independent t-test. Reference Listings: 16.2.1.3, 16.2.4.1, 16.2.9.3

Output Generated on: DDMMMYYYY hh:mm

<Note: Repeat the same table as 14.1.2 for Safety set and 14.1.3 for PK set >

Project No. 0110-23 Version 00

14.1.4 Visit wise distribution of subjects (Randomized set)

Lambda Therapeutic Research Ltd. Confidential Project No. 0110-23

Table 14.1.4

Visit wise distribution of subjects (Randomized set)

Visits	TRTR (N=xx)	RTRT (N=xx)	Total (N=xx)
	n (%)	n (%)	n (%)
PERIOD 1 (Day-1)	xx (xx.x)	xx (xx.x)	xx (xx.x)
PERIOD 2 (Day-1)	xx (xx.x)	xx (xx.x)	xx (xx.x)
PERIOD 3 (Day-1)	xx (xx.x)	xx (xx.x)	xx (xx.x)
PERIOD 4 (Day-1)	xx (xx.x)	xx (xx.x)	xx (xx.x)

N = Number of subjects in safety set, n = Number of subjects in respective categories Note: Percentages are calculated based on the total number of subjects in each category. Treatment specification -> T = Test Product and R = Reference Product. Reference Listing: 16.2.1.3, 16.2.9.7

Output Generated on: DDMMMYYYY hh:mm

<Note: Repeat the same table as 14.1.5 for Safety set and 14.1.6 for PK set.>

Project No. 0110-23 Version 00

14.1.7 Summary of protocol deviations

Lambda Therapeutic Research Ltd.

Confidential
Table No. 14.1.7
Summary of protocol deviations

Project No. 0110-23

Protocol deviation	Type of Proto	Total	
FIOLOCOI deviación	Major	Minor	iotai
Subjects with protocol deviations	XX	XX	xx
At least one protocol deviation	xx	xx	xx
Dosing Related	xx	XX	XX
IMP Related	xx	xx	xx
Lab Related	xx	XX	XX
Others	xx	xx	xx
•			

Reference Listing: 16.2.2

Output Generated on: DDMMMYYYY hh:mm

Project No. 0110-23 Version 00

14.2 Pharmacokinetic Data 14.2.1 Plasma Albendazole Data

14.2.1.1 Summary statistics of pharmacokinetic parameters for albendazole

Lambda Therapeutic Research Ltd. Confidential Project No. 0110-23 The SAS System Version 9.4 Table No. 14.2.1.1 Sponsor: GSK Research & Development

Summary statistics of pharmacokinetic parameters for albendazole $% \left(\frac{1}{2}\right) =\frac{1}{2}\left(\frac{1}{2}\right) +\frac{1}{2}\left(\frac{1}{2}\right) +\frac{1}{2}\left($

Albendazole Tablets IP 400 mg

Measures	Tmax	Cmax	AUC0-t
	(unit)	(unit)	(unit)
Test Treatment-T			
N	XX	xx	XX
Mean	XX.XX	XX.XXX	xx.xxx
SD	XX.XXX	XX.XXXX	XX.XXXX
CV (%)	XX.X	XX.X	XX.X
Geometric Mean	XX.XX	XX.XXX	XX.XXX
Reference Treatment-R			
N	XX	XX	XX
Mean	XX.XX	XX.XXX	XX.XXX
SD	xx.xxx	XX.XXXX	xx.xxxx
CV (%)	xx.x	XX.X	XX.X
Geometric Mean	XX.XX	XX.XXX	XX.XXX
ANOVA p-value			
 ln-transformed Sequence	_	x.xxxx	x.xxxx
Period	_	X.XXXX	x.xxxx
Formulation	_	X.XXXX	x.xxxx
D = + 1 = 1 = + (Q = =)			
Participant (Sequence) Geometric Least Squares Means	_	x.xxx	x.xxx
Geometric Least Squares Means	-	x.xxxx xxxx.xxx	x.xxxx xxxx.xxx
Geometric Least Squares Means	- - -		
Geometric Least Squares Means In-transformed Test-T Reference-R Ratio of Geometric Least Squares Mea	- - ns(%)(T/R)	xxxx.xxx	xxxx.xxx
Geometric Least Squares Means In-transformed Test-T Reference-R Ratio of Geometric Least Squares Mea	- - ns(%)(T/R)	xxxx.xxx	xxxx.xxx
Geometric Least Squares Means ln-transformed Test-T		xxxx.xxx xxxx.xxx	xxxx.xxx xxxx.xxx
Geometric Least Squares Means In-transformed Test-T Reference-R Ratio of Geometric Least Squares Means In-transformed Intra subject Variability of Referen		xxxx.xxx xxxx.xxx	xxxx.xxx xxxx.xxx
Geometric Least Squares Means In-transformed Test-T Reference-R Ratio of Geometric Least Squares Means In-transformed Intra subject Variability of Referen In-transformed	 - ce Formulati -	xxxx.xxx xxxx.xxx xxx.x on-R(%)	xxxx.xxx xxxx.xxx xxx.x
Geometric Least Squares Means In-transformed Test-T Reference-R Ratio of Geometric Least Squares Means In-transformed Intra subject Variability of Referen	 - ce Formulati -	xxxx.xxx xxxx.xxx xxx.x on-R(%)	xxxx.xxx xxxx.xxx xxx.x
Geometric Least Squares Means In-transformed Test-T Reference-R Ratio of Geometric Least Squares Mea In-transformed Intra subject Variability of Referen In-transformed Within subject standard deviation of In-transformed	 - ce Formulati -	xxxx.xxx xxxx.xx xxx.x on-R(%) xx.x ormulation-R (SW	xxxx.xxx xxxx.xx xxx.x xx.x
Geometric Least Squares Means In-transformed Test-T Reference-R Ratio of Geometric Least Squares Mea In-transformed Intra subject Variability of Referen In-transformed Within subject standard deviation of In-transformed	 - ce Formulati -	xxxx.xxx xxxx.xx xxx.x on-R(%) xx.x ormulation-R (SW	xxxx.xxx xxxx.xx xxx.x xx.x
Geometric Least Squares Means In-transformed Test-T Reference-R Ratio of Geometric Least Squares Mea In-transformed Intra subject Variability of Referen In-transformed Within subject standard deviation of In-transformed 90% Confidence Interval (T Vs. R) In-transformed Lower	 - ce Formulati -	xxxx.xxx xxxx.xx xxx.x on-R(%) xx.x ormulation-R (SW	xxxx.xxx xxx.x xxx.x xx.x xx.x
Geometric Least Squares Means In-transformed Test-T Reference-R Ratio of Geometric Least Squares Mea In-transformed Intra subject Variability of Referen In-transformed Within subject standard deviation of In-transformed 90% Confidence Interval (T Vs. R) In-transformed Lower Upper	 - ce Formulati -	xxxx.xxx xxxx.xxx xxx.x on-R(%) xx.x ormulation-R (SW xx.x	xxxx.xxx xxx.x xxx.x xxx.x xx.x xx.x
Geometric Least Squares Means In-transformed Test-T Reference-R Ratio of Geometric Least Squares Mea In-transformed Intra subject Variability of Referen In-transformed Within subject standard deviation of In-transformed 90% Confidence Interval (T Vs. R) In-transformed Lower	 - ce Formulati -	xxxx.xxx xxxx.xxx xxx.x on-R(%) xx.x ormulation-R (SW xx.x xx.x	xxxx.xxx xxx.xx xxx.x xx.x xx.x xx.x xx.x

Output Generated on: DDMMMYYYY hh:mm

<Note: Repeat the same table as 14.2.2.1 for albendazole sulfoxide >

14.2.1.2 Pharmacokinetic parameters (untransformed) of albendazole for Test Product-T and Reference Product-R

Lambda Therapeutic Research Ltd.

Confidential

Project No. 0110-23

Table No. 14.2.1.2

Pharmacokinetic parameters (untransformed) of albendazole for Test Product-T and Reference Product-R												
		Tmax	(unit)	Cmax (unit)			A	UC0-t (uni	t)	AUC0-inf (unit)		
Participants S	Sequence	Formu	ılation	Formulation			I	Formulation	1	Formulation		
		T	R	T	R	(T/R)%	T	R	(T/R)%	T	R	(T/R)%
1001		XX.XX	XX.XX	XX.XXX	XX.XXX	XX.X	XX.XXX	XX.XXX	XX.X	XX.XXX	XX.XXX	XX.X
1002		XX.XX	XX.XX	XX.XXX	XX.XXX	XX.X	XX.XXX	XX.XXX	XX.X	XX.XXX	XX.XXX	XX.X
				•	•	•	•		•	•	•	•
				•	•	•	•		•	•	•	•
		•	•									
n		XX.XX	XX.XX	XX.XXX	XX.XXX	XX.X	XX.XXX	XX.XXX	XX.X	XX.XXX	XX.XXX	XX.X
N	N		XX	XX	XX	-	XX	XX	-	XX	XX	-
Mean		XX.XX	XX.XX	XX.XXX	XX.XXX	-	XX.XXX	XX.XXX	-	XX.XXX	XX.XXX	-
95% CI of arit	hmetic	X.XX-	x.xx-	x.xxx-	x.xxx-	-	x.xxx-	x.xxx-	-	x.xxx-	x.xxx-	-
mean		X.XX	X.XX	X.XXX	X.XXX		X.XXX	X.XXX		X.XXX	X.XXX	
SD		XX.XXX	XX.XXX	XX.XXXX	XX.XXXX	-	XX.XXXX	XX.XXXX	-	XX.XXXX	XX.XXXX	-
Min		XX.XX	XX.XX	XX.XXX	XX.XXX	-	XX.XXX	XX.XXX	-	XX.XXX	XX.XXX	-
Median	1	XX.XX	XX.XXX	XX.XXX	XX.XXX	-	XX.XXX	XX.XXX	-	XX.XXX	XX.XXX	-
Max		XX.XX	XX.XX	XX.XXX	XX.XXX	-	XX.XXX	XX.XXX	-	XX.XXX	XX.XXX	-
CV%		XX.X	XX.X	XX.X	XX.X	-	XX.X	XX.X	-	XX.X	XX.X	-
Geometric Mean		XX.XX	XX.XX	XX.XXX	XX.XXX	-	XX.XXX	XX.XXX	-	XX.XXX	XX.XXX	-
95% CI of geome	etric mean	X.XX- X.XX	X.XX-	X.XXX-	X.XXX-	-	X.XXX-	X.XXX-	-	X.XXX-	X.XXX-	-
al a D			X.XX	X.XXX	X.XXX		X.XXX	X.XXX		X.XXX	X.XXX	

Note: Repeat the same table as 14.2.2.2 for albendazole sulfoxide.>

14.2.1.2 Contd 1. Pharmacokinetic parameters (untransformed) of albendazole for Test Product-T and Reference Product-R

Lambda Therapeutic Research Ltd.

Confidential

Project No. 0110-23

Table No. 14.2.1.2 Contd.

Pharmacokinetic parameters (untransformed) of albendazole for Test Product-T and Reference Product-R

		AUC_%Extr	ap_obs (%)	Lambda	a_z (unit)	t1/2 (unit)		
Participants	Sequence	Formul	ation	Form	ulation	Formulation		
		Т	R	T	R	Т	R	
1001	1001		XX.XXX	XX.XXX	XX.XXX	XX.XXX	xx.xxx	
1002		XX.XXX	XX.XXX	XX.XXX	XX.XXX	XX.XXX	xx.xxx	
					•			
			•	•		•		
			•	•		•		
n		XX.XXX	XX.XXX	XX.XXX	XX.XXX	XX.XXX	XX.XXX	
	N		XX	XX	XX	XX	XX	
N	Mean		XX.XXX	XX.XXX	XX.XXX	XX.XXX	XX.XXX	
95%	95% CI of		x.xxx-	x.xxx-	x.xxx-	x.xxx-	x.xxx-	
arithme	etic mean	X.XXX	x.xxx	X.XXX	X.XXX	X.XXX	x.xxx	
	SD		XX.XXXX	XX.XXXX	XX.XXXX	XX.XXXX	XX.XXXX	
]	Min		XX.XXX	XX.XXX	XX.XXX	XX.XXX	XX.XXX	
Med	Median		XX.XXX	XX.XXX	XX.XXX	XX.XXX	XX.XXX	
I	Max		XX.XXX	XX.XXX	XX.XXX	XX.XXX	xx.xxx	
	CV%		XX.X	XX.X	XX.X	XX.X	XX.X	
Geom	Geometric Mean		XX.XXX	XX.XXX	XX.XXX	XX.XXX	xx.xxx	
95% CI of ge	95% CI of geometric mean		x.xxx-	x.xxx-	x.xxx-	x.xxx-	x.xxx-	
		X.XXX	X.XXX	x.xxx x.xxx		X.XXX	X.XXX	

<Note: Repeat the same table as 14.2.2.2 for albendazole sulfoxide.>

14.2.1.3 Individual Pharmacokinetic parameter (untransformed) of albendazole for Test Product-T1 (first administration), Test Product-T2 (second administration), Reference Product-R1 (first administration) and Reference Product-R2 (second administration)

Lambda Therapeutic Research Ltd.

Confidential Table No. 14.2.1.3

Project No. 0110-23

Individual pharmacokinetic parameters (untransformed) of albendazole for Test Product-T1 (first administration), Test Product-T2 (second administration), Reference Product-R1 (first administration) and Reference Product-R2 (second administration)

			Tmax ((unit)			Cmax (ur	nit)		AUC0-t (unit)			
Participants	Sequence		Formu	ation			Formulat	ion		Formulation			
		T1	T2	R1	R2	T1	T2	R1	R2	T1	T2	R1	R2
1001		XX.XX	XX.XX	XX.XX	XX.XX	XX.XXX	XX.XXX	XX.XXX	XX.XXX	XX.XXX	XX.XXX	XX.XXX	XX.XXX
1002		xx.xx	XX.XX	XX.XX	XX.XX	XX.XXX	xx.xxx	XX.XXX	XX.XXX	XX.XXX	xx.xxx	xx.xxx	xx.xxx
			•	•	•	•		•	•	•			
•			•	•	•	•		•	•	•			•
n		XX.XX	XX.XX	XX.XX	XX.XX	XX.XXX	XX.XXX	XX.XXX	XX.XXX	XX.XXX	XX.XXX	XX.XXX	XX.XXX
N		XX	XX	XX	XX	XX	XX	XX	XX	XX	XX	XX	XX
Mea	an	XX.XX	XX.XXX	XX.XX	XX.XX	XX.XXX	XX.XXX	XX.XXX	XX.XXX	XX.XXX	XX.XXX	XX.XXX	XX.XXX
95% CI of a	arithmetic	X.XX-	X.XXX-	X.XX-X.XX	X.XX-X.XX	X.XXX-	x.xxx-	X.XXX-	X.XXX-	X.XXX-	x.xxx-	x.xxx-	X.XXX-
mea	ın	X.XX	X.XXX			X.XXX	X.XXX	X.XXX	X.XXX	X.XXX	X.XXX	X.XXX	X.XXX
SE)	xx.xxx	XX.XXXX	XX.XXX	XX.XXX	XX.XXXX	XX.XXXX	xx.xxxx	XX.XXXX	XX.XXXX	xx.xxxx	XX.XXXX	XX.XXXX
Mi	n	XX.XX	XX.XXX	XX.XX	XX.XX	XX.XXX	XX.XXX	XX.XXX	XX.XXX	XX.XXX	XX.XXX	XX.XXX	XX.XXX
Med	ian	xx.xxx	XX.XXX	XX.XXX	XX.XXX	XX.XXX	XX.XXX	XX.XXX	XX.XXX	XX.XXX	XX.XXX	XX.XXX	XX.XXX
Ma	X	xx.xx	XX.XXX	XX.XX	XX.XX	XX.XXX	xx.xxx	XX.XXX	XX.XXX	XX.XXX	xx.xxx	XX.XXX	XX.XXX
CV	%	XX.X	XX.X	XX.X	XX.X	XX.X	XX.X	XX.X	XX.X	XX.X	XX.X	XX.X	XX.X
Geometri	c Mean	xx.xx	XX.XXX	XX.XX	XX.XX	XX.XXX	xx.xxx	XX.XXX	XX.XXX	XX.XXX	xx.xxx	xx.xxx	xx.xxx
95% CI of §	geometric	x.xx-	X.XXX-	X.XX-X.XX	x.xx-x.xx	X.XXX-	x.xxx-	x.xxx-	x.xxx-	x.xxx-	x.xxx-	x.xxx-	x.xxx-
mea	nn	X.XX	X.XXX	1 10 11 2		X.XXX	X.XXX	X.XXX	X.XXX	X.XXX	X.XXX	X.XXX	X.XXX

<Note: Repeat the same table as 14.2.2.3 for albendazole sulfoxide >

14.2.1.3 Contd. Individual pharmacokinetic parameter (untransformed) of albendazole for Test Product-T1 (first administration), Test Product-T2 (second administration), Reference Product-R1 (first administration) and Reference Product-R2 (second administration)

Lambda Therapeutic Research Ltd.

Confidential

Project No. 0110-23

Table No. 14.2.1.3 Contd.

Individual pharmacokinetic parameters (untransformed) of albendazole for Test Product-T1 (first administration), Test Product-T2 (second administration), Reference Product-R1 (first administration) and Reference Product-R2 (second administration)

			AUC0-inf	(unit)		AUC_%Extrap_obs (%)					
Participants	Sequence		Formulatio	on		Formulation					
		T1	T2	R1	R2	T1	T2	R1	R2		
1001		XX.XXX	XX.XXX	XX.XXX	XX.XXX	XX.XXX	XX.XXX	XX.XXX	XX.XXX		
1002		XX.XXX	XX.XXX	XX.XXX	XX.XXX	XX.XXX	XX.XXX	XX.XXX	XX.XXX		
		•	•	•	•		•	•			
n		XX.XXX	XX.XXX	XX.XXX	XX.XXX	XX.XXX	XX.XXX	XX.XXX	XX.XXX		
	N		XX	XX	XX	XX	XX	XX	XX		
	Mean		XX.XXX	XX.XXX	XX.XXX	XX.XXX	XX.XXX	XX.XXX	XX.XXX		
95% CL c	95% CI of arithmetic mean		X.XXX-	X.XXX-	x.xxx-	x.xxx-	X.XXX-	x.xxx-	x.xxx-x.xxx		
7570 61 6			X.XXX	X.XXX	X.XXX	X.XXX	X.XXX	X.XXX			
	SD		XX.XXXX	XX.XXXX	XX.XXXX	xx.xxxx	XX.XXXX	XX.XXXX	XX.XXXX		
	Min		XX.XXX	XX.XXX	xx.xxx	XX.XXX	XX.XXX	XX.XXX	XX.XXX		
	Median		XX.XXX	XX.XXX	xx.xxx	XX.XXX	XX.XXX	XX.XXX	XX.XXX		
	Max		XX.XXX	XX.XXX	XX.XXX	XX.XXX	XX.XXX	XX.XXX	XX.XXX		
CV%		XX.X	XX.X	XX.X	XX.X	XX.X	XX.X	XX.X	XX.X		
Geomet	Geometric Mean		XX.XXX	XX.XXX	XX.XXX	XX.XXX	XX.XXX	XX.XXX	XX.XXX		
95% CL	95% CI of geometric mean		x.xxx-	x.xxx-	x.xxx-	x.xxx-	x.xxx-	x.xxx-	X.XXX-X.XXX		
9370 CT C		X.XXX	X.XXX	X.XXX	X.XXX	X.XXX	X.XXX	X.XXX			

<Note: Repeat the same table as 14.2.2.3 for albendazole sulfoxide >

14.2.1.3 Contd. Individual pharmacokinetic parameter (untransformed) of albendazole for Test Product-T1 (first administration), Test Product-T2 (second administration), Reference Product-R1 (first administration) and Reference Product-R2 (second administration)

Lambda Therapeutic Research Ltd.

Confidential

Project No. 0110-23

Table No. 14.2.1.3 Contd.

Individual pharmacokinetic parameters (untransformed) of albendazole for Test Product-T1 (first administration), Test Product-T2 (second administration), Reference Product-R1 (first administration) and Reference Product-R2 (second administration)

	Sequence		Lambda	a_z (unit)		t1/2 (unit)					
Participants			Form	ulation		Formulation					
		T1	T2	R1	R2	T1	T2	R1	R2		
1001		XX.XXX	XX.XXX	XX.XXX	XX.XXX	XX.XXX	XX.XXX	XX.XXX	XX.XXX		
1002		XX.XXX	XX.XXX	XX.XXX	XX.XXX	xx.xxx	XX.XXX	XX.XXX	XX.XXX		
		•	•	•		•	•	•			
n		XX.XXX	XX.XXX	XX.XXX	XX.XXX	XX.XXX	XX.XXX	XX.XXX	XX.XXX		
N	N		XX	XX	XX	XX	XX	XX	XX		
Mear	Mean		XX.XXX	XX.XXX	XX.XXX	XX.XXX	XX.XXX	XX.XXX	XX.XXX		
95% CI of arithmetic mean		X.XXX-	X.XXX-	X.XXX-	x.xxx-	x.xxx-	X.XXX-	x.xxx-	x.xxx-x.xxx		
	7570 CI of artifificate mean		X.XXX	X.XXX	X.XXX	X.XXX	X.XXX	X.XXX			
SD	SD		XX.XXXX	XX.XXXX	XX.XXXX	XX.XXXX	XX.XXXX	XX.XXXX	XX.XXXX		
Min	Min		XX.XXX	XX.XXX	XX.XXX	xx.xxx	XX.XXX	XX.XXX	XX.XXX		
Media	Median		XX.XXX	XX.XXX	XX.XXX	XX.XXX	XX.XXX	XX.XXX	XX.XXX		
Max		XX.XXX	XX.XXX	XX.XXX	XX.XXX	XX.XXX	XX.XXX	XX.XXX	XX.XXX		
CV%		XX.X	XX.X	XX.X	XX.X	XX.X	XX.X	XX.X	XX.X		
Geometric	Geometric Mean		XX.XXX	XX.XXX	XX.XXX	xx.xxx	XX.XXX	XX.XXX	XX.XXX		
95% CI of geon	netric mean	x.xxx-	x.xxx-	x.xxx-	x.xxx-	x.xxx-	x.xxx-	x.xxx-	X.XXX-X.XXX		
7570 CI 01 gcon	ileti ie ilieali	X.XXX	X.XXX	X.XXX	X.XXX	X.XXX	X.XXX	X.XXX			

<Note: Repeat the same table as 14.2.2.3 for albendazole sulfoxide >

14.2.1.4 Pharmacokinetic parameters (untransformed) of data excluded from statistical analysis for albendazole (if applicable)

Lambda Therapeutic Research Ltd.

Project No. 0110-23

Table No. 14.2.1.4

Confidential

Pharmacokinetic parameters (untransformed) of data excluded from statistical analysis for albendazole

Participants	Period	Sequence	Formulation	Tmax (unit)	Cmax (unit)	AUC0-t (unit)	AUC0-inf (unit)	AUC_%Extrap_obs (%)	Lambda_z (unit)	t1/2 (unit)
1001				XX.XXX	XX.XXX	xx.xxx	XX.XXX	xx.xxx	xx.xxx	xx.xx
1002				xx.xxx	xx.xxx	xx.xxx	XX.XXX	XX.XXX	xx.xxx	xx.xx
						•				
						•	•		•	
						•	•	•	•	
								•		
n				xx.xxx	xx.xxx	xx.xxx	XX.XXX	xx.xxx	xx.xxx	xx.xx

<Note: Repeat the same table as 14.2.2.4 for albendazole sulfoxide.>

14.2.1.5 Pharmacokinetic parameters (In-transformed) of albendazole for Test Product-T and Reference Product-R

Lambda Therapeutic Research Ltd.

Confidential

Project No. 0110-23

Table No. 14.2.1.5

Pharmacokinetic parameters (In-transformed) of albendazole for Test Product-T and Reference Product-R

		Cma	ax	Α	AUC0-t	
Participants	Sequence	Formul	ation	Formulation		
		T	R	T	R	
1001		XX.XXX	XX.XXX	XX.XXX	XX.XXX	
1002		XX.XXX	XX.XXX	XX.XXX	XX.XXX	
n		XX.XXX	XX.XXX	XX.XXX	XX.XXX	
N		XX	XX	XX	XX	
Mean	ı	XX.XXX	XX.XXX	XX.XXX	XX.XXX	
95% CI of arithr	netic mean	X.XXX-X.XXX	x.xxx-x.xxx	x.xxx-x.xxx	X.XXX-X.XXX	
SD		XX.XXXX	XX.XXXX	XX.XXXX	XX.XXXX	
Min		XX.XXX	XX.XXX	XX.XXX	XX.XXX	
Media	n	XX.XXX	XX.XXX	XX.XXX	XX.XXX	
Max		XX.XXX	XX.XXX	XX.XXX	XX.XXX	
CV%		XX.X	XX.X	XX.X	XX.X	
Geometric M	ean	XX.XXX	XX.XXX	XX.XXX	XX.XXX	
95% CI of geom	netric mean	X.XXX-X.XXX	X.XXX-X.XXX	X.XXX-X.XXX	X.XXX-X.XXX	

<Note: Repeat the same table as 14.2.2.5 for albendazole sulfoxide.>

14.2.1.6 Individual Pharmacokinetic parameter (In-transformed) of albendazole for Test Product-T1 (first administration), Test Product-T2 (second administration), Reference Product-R1 (first administration) and Reference Product-R2 (second administration)

Lambda Therapeutic Research Ltd.

Confidential

Project No. 0110-23

Table No. 14.2.1.6

Individual pharmacokinetic parameters (In-transformed) of albendazole for Test Product-T1 (first administration), Test Product-T2 (second administration), Reference Product-R1 (first administration) and Reference Product-R2 (second administration)

		Cr	nax (unit)			AUC0-t (unit)			
Participants	Sequence	Fo	rmulation			Formulation			
		T1	T2	R1	R2	T1	T2	R1	R2
1001		xx.xxx	XX.XXX	XX.XXX	XX.XXX	XX.XXX	XX.XXX	xx.xxx	XX.XXX
1002		XX.XXX	xx.xxx	xx.xxx	xx.xxx	xx.xxx	xx.xxx	XX.XXX	XX.XXX
			•	•	•		•	•	
•		•	•	•	•	•	•	•	
			•	•	•	•	•	•	•
n		XX.XXX	XX.XXX	XX.XXX	XX.XXX	XX.XXX	XX.XXX	XX.XXX	XX.XXX
	N	XX	XX	XX	XX	XX	XX	XX	XX
ı	Mean	XX.XXX	xx.xxx	xx.xxx	xx.xxx	xx.xxx	xx.xxx	XX.XXX	XX.XXX
95% CI of a	arithmetic mean	x.xxx-x.xxx	x.xxx-x.xxx	x.xxx-x.xxx	x.xxx-x.xxx	x.xxx-x.xxx	x.xxx-x.xxx	x.xxx-x.xxx	x.xxx-x.xxx
	SD	xx.xxxx	xx.xxx	xx.xxx	xx.xxx	xx.xxx	xx.xxxx	xx.xxx	XX.XXXX
	Min	XX.XXX	xx.xxx	XX.XXX	xx.xxx	XX.XXX	XX.XXX	XX.XXX	XX.XXX
M	Iedian	XX.XXX	XX.XXX	XX.XXX	XX.XXX	XX.XXX	XX.XXX	XX.XXX	XX.XXX
	Max	XX.XXX	XX.XXX	XX.XXX	XX.XXX	XX.XXX	XX.XXX	XX.XXX	XX.XXX
	CV%	XX.X	XX.X	XX.X	XX.X	XX.X	XX.X	XX.X	XX.X
Geom	etric Mean	XX.XXX	XX.XXX	xx.xxx	XX.XXX	xx.xxx	XX.XXX	XX.XXX	XX.XXX
95% CI of §	geometric mean	x.xxx-x.xxx	x.xxx-x.xxx	x.xxx-x.xxx	x.xxx-x.xxx	x.xxx-x.xxx	X.XXX-X.XXX	x.xxx-x.xxx	x.xxx-x.xxx

<Note: Repeat the same table as 14.2.2.6 for albendazole sulfoxide.>

